4.4. Decay Characteristics

The time course of radioactive decay for Fluorine [¹⁸F] is shown below

Min.	Fraction Remaining
0	1.000
30	0.827
60	0.685
90	0.567
120	0.469
150	0.388
180	0.321
210	0.266
240	0.220

Physical decay chart for Fluorine [¹⁸F]. Half-life = 109.77 min.

4.5. Formulation and Dose Florbetapir F 18 Injection

Drug Product is formulated in 10% v/v ethanol, USP, 0.45% sodium ascorbate, USP, in 0.9% sodium chloride injection, USP. Subjects will receive a single IV administration of approximately 370 MBq (10 mCi) of Florbetapir F 18 Injection immediately prior to imaging. The mass dose of florbetapir in each human dose will be \leq 50 μ g (0.14 μ mol) per 10 mCi dose in total volume not exceeding 10 mL. Florbetapir F 18 Injection expires at 10 hours post End-of-Synthesis (EOS) or when either the strength or specific activity shelf-life specifications (Not less than (NLT) 37 MBq/mL (1 mCi/ml) or NLT 7.4 MBq/ μ g (0.2mCi/ μ g), respectively) are met, whichever is soonest.

Florbetapir F 18 Injection will be supplied from manufacturing facilities approved for commercial distribution under NDA 202-008.

4.6. Formulation and Dose ¹⁸F-AV-1451 Injection

¹⁸F-AV-1451 Injection is a clear solution containing ¹⁸F-AV-1451 (drug substance) formulated for intravenous bolus administration. Depending on the manufacturer, ¹⁸F-AV-1451 Injection will be formulated in:

- aqueous 21 mM sodium phosphate solution containing up to 10% (v/v) ethanol, or
- a solution containing 10% (v/v) ethanol, USP in 0.9% sodium chloride injection, USP.

Drug product of either formulation is manufactured to meet one common set of specifications.

The expiration time and date of ¹⁸F-AV-1451 Injection are provided on the outer label of each dose based on specific activity or strength. ¹⁸F-AV-1451 Injection should be stored at room temperature.

4.7. Packaging Florbetapir F 18 Injection

Unit doses of Drug Product may be contained in a sterile, apyrogenic 10, 30 or 50 mL clear Type I Borosilicate glass serum vial closed with a 20 mm Fluro Tec®-coated 4432/50-B2-40 gray elastomeric closure sealed with a 20 mm aluminum crimp seal, manufactured by Allergy Laboratories or may be contained in 2 mL, 5 mL, or 10 mL sterile apyrogenic NORM-JECT® polypropylene/high-density polyethylene syringes.

4.8. Packaging ¹⁸F-AV-1451 Injection

Each package of ¹⁸F-AV-1451 Injection includes a sterile apyrogenic sealed glass vial or sterile apyrogenic syringe containing ¹⁸F-AV-1451 Injection, a surrounding protective lead shield canister, and an outside delivery case.

4.9. Storage and Handling Florbetapir F 18 Injection

Florbetapir F 18 Injection is stored at 25°C; excursions permitted to 15-30°C. The product does not contain a preservative. Florbetapir F 18 Injection should be stored within the original container or equivalent radiation shielding. Florbetapir F 18 Injection must not be diluted.

4.10. Storage and Handling ¹⁸F-AV-1451 Injection

¹⁸F-AV-1451 Injection is stored at room temperature. ¹⁸F-AV-1451 Injection should be stored within the original container or equivalent radiation shielding. ¹⁸F-AV-1451 Injection must not be diluted.

5. INVESTIGATIONAL PLAN

5.1. Overall Design and Plan of Trial

This is a phase 2 cross-sectional and longitudinal observational study that will evaluate imaging characteristics of ¹⁸F-AV-1451 in control subjects and patients with MCI and AD. This study will be conducted in two phases, an exploratory/hypothesis generating phase and a confirmatory/validation phase, which will have separate subjects and analyses. Approximately 230 subjects will be enrolled in the Exploratory Phase of the study: 80 cognitively healthy volunteers, 80 subjects with MCI, 70 subjects with AD. Approximately 20 cognitively healthy volunteers will be ≥ 20 to ≤ 40 years of age. Approximately 60 cognitively healthy volunteers will be ≥ 50 years of age and will be distributed across age deciles (50-59, 60-69, 70-79 and ≥ 80). Approximately 150 subjects with cognitive impairment will be enrolled in the Confirmatory Phase.

All subjects will provide informed consent before starting any study procedures.

For both the Exploratory and Confirmatory Phases, screening assessments may take place over several days and will include demographic information, cognitive testing, safety assessment, and MRI, including both volumetric and standard clinical sequences. Raters administering the cognitive testing will be blinded to the ¹⁸F-AV-1451 scans for subjects in the Confirmatory Cohort. Subjects who qualify for the study will undergo both a florbetapir F 18 PET imaging session and an ¹⁸F-AV-1451 PET imaging session. Some subjects, who are ≥ 50 years of age, in the Exploratory Phase will have the option to participate in cerebrospinal fluid (CSF) collection by lumbar puncture (LP).

Subjects who are ≥ 50 years of age will return for follow-up visits at 9 (+/-2) months and 18 (+/-2) months following the initial ¹⁸F-AV-1451 scan. Cognitive assessments and updates to concomitant medications and medical history will be collected at each follow-up visit. Subjects in the Exploratory Phase will also have follow up ¹⁸F-AV-1451 scans and MRI, including both volumetric and standard clinical sequences. A sub-set of subjects in the Exploratory Phase may have the option to have an additional resting state functional (rsf)MRI sequence scan in addition to the volumetric and standard clinical sequences at both the screening MRI and follow-up MRIs. All follow-up procedures should be collected within the specified visit window (See Section 7.1.4). Subjects or their designated decision maker will be contacted by phone at 5 and 14 months following the initial ¹⁸F-AV-1451 scan to collect updated concomitant medications and medical history.

Avid personnel will be blinded to the Confirmatory Phase longitudinal cognitive data. Avid personnel will also remain blinded to the PET scans (both florbetapir and ¹⁸F-AV-1451) performed on subjects in the Confirmatory Phase with the exception of periodic quality assurance (QA) assessments of a random subset of image data (not to exceed 20% unless issues identified that warrant additional review). These QA reviews will serve to ensure image quality and data integrity for the scans collected and managed by the imaging core laboratory. Avid staff performing the PET scan QA assessment will not be aware of diagnostic group or cognitive test scores for the subjects/images being reviewed.

Florbetapir F 18 PET Imaging Session:

For the florbetapir F 18 PET imaging session, an intravenous catheter will be placed for IV administration of Florbetapir F 18 Injection. Subjects will receive a single IV bolus injection target dose of 370 MBq (10 mCi) of Florbetapir F 18 Injection followed by a saline flush. At approximately 50 minutes following injection, a continuous 10-minute brain scan (2 acquisitions of 5 minute duration) will begin.

Adverse events will be continuously monitored during the florbetapir F 18 PET imaging session. A physician or physician designee must evaluate the subject for adverse events prior to injection and prior to discharge from the imaging center. Subjects who experience an adverse event will not be discharged from the imaging center until the event has resolved or stabilized.

A follow-up phone call to the subject, or designated decision maker, will be conducted between 2 or 3 business days of the post-injection of florbetapir F 18, but not before 48 hours post-injection, to confirm subject well-being and to collect information about any new adverse events. If both of these days are not business days, the follow-up phone call can occur the following business day.

¹⁸F-AV-1451 PET Imaging Session(s):

For the ¹⁸F-AV-1451 PET imaging session(s), an intravenous catheter will be placed for IV administration of ¹⁸F-AV-1451 Injection. Subjects will receive a single IV bolus injection target dose of 370 MBq (10 mCi) of ¹⁸F-AV-1451 Injection followed by a saline flush. At approximately 80 minutes post dose, a continuous 20-minute brain scan (4 acquisitions of 5-minute duration) will be obtained. If at any point during the imaging session it is determined that the subject is not able to continue, or that it is not in the best interest of the subject to continue, imaging will be discontinued. The image data that has been collected up to that point will be analyzed. Clinical laboratory tests will be obtained prior to injection and upon completion of each imaging session. Adverse events will be monitored continuously during the imaging session. Subjects who experience any adverse event during an imaging session will not be discharged until the event has resolved or stabilized.

A follow-up phone call to the subject, or designated decision maker, will be conducted between 2 or 3 business days of the imaging day, but not before 48 hours post-injection, to confirm subject well-being and to collect information about any new adverse events. If both of these days are not business days, the follow-up phone call can occur the following business day.

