7. PROCEDURES AND METHODS

7.1. Assessment Periods

See Section 11.2, Trial Flow Charts.

This study will be comprised of a cross-sectional component and a longitudinal component. Subjects in both the Exploratory Phase and Confirmatory Phase will have screening visit(s), a florbetapir F 18 PET imaging visit, a ¹⁸F-AV-1451 PET imaging visit, and follow-up phone calls after each imaging visit. Subjects who are ≥ 50 years old will return for follow-up visits at 9 (+/-2) and 18 (+/-2) months following the initial ¹⁸F-AV-1451 scan. Cognitive assessments and updates to concomitant medications and medical history will be collected at each follow-up visit. Subjects in the Exploratory Phase will also have follow-up ¹⁸F-AV-1451 scans and MRI.

7.1.1. Screening and Baseline Visit:

Screening may take place over several days. All screening assessments should be performed within 30 days of the initial ¹⁸F-AV-1451 PET imaging session.

Screening assessments will include:

- Informed consent;

- Demographics (age, gender, race, ethnicity, education, alcohol, drug use, and smoking);
- Medical history, physical and neurological exam, concomitant medications;
- Disease history (date/months since symptom onset, date/months since diagnosis, family history of neurologic disease) for cognitively impaired subjects;
- Ohio State University Traumatic Brain Injury Identification Method (OSU TBI-ID);
- Mini Mental State Exam (MMSE);
- Safety assessments: Vital signs (pulse rate, respiratory rate, supine blood pressure, height and weight), ECG, safety labs(hematology, chemistry, and urinalysis);
- Serum beta-hCG test (for females of childbearing potential defined as pre-menopausal or less than 2 years post-menopausal and not surgically sterile);
- MRI imaging including standard clinical sequences and volumetric MRI;
- A physician will see the patient during the screening visit.

Baseline assessments may be performed at the screening visit or +/- 30 days of the initial ¹⁸F-AV-1451 Imaging Visit. Raters administering the MMSE and baseline assessments described below will be blinded to the ¹⁸F-AV-1451 scans for subjects in the Confirmatory Cohort.

Baseline assessments will include:

- Alzheimer's Disease Assessment Scale- Cognitive subscale (ADAS-Cog11);

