- Neuropsychological test battery (Digit Symbol Substitution Test (DSST), Digit span forward and backward ,Trail Making A and B, Logical Memory Test, Immediate and Delayed Recall Story A , Animal list generation, Boston Naming Test (BNT) (30 item), American National Adult Reading Test (ANART), Clock Drawing Test, Benton Judgment of Line Orientation test);
- Subjects in the Confirmatory Cohort will also be administered the Clinical Dementia Rating (CDR) Scale;
- Pfeffer Functional Activities Questionnaire (FAQ). For the MCI and AD groups only.

7.1.2. Optional Cerebrospinal fluid (CSF) collection by Lumbar Puncture (LP) (A β , p-tau, t-tau); Exploratory Phase only

Some subjects (depending on site participation) who are \geq 50 years of age who qualify for the study will be offered to consent for optional CSF collection by LP. The LP should be performed at least 48 hours apart from the PET imaging sessions and should be performed within +/- 60 days of the initial ¹⁸F-AV-1451 Imaging Visit. Each LP will be done by a qualified physician who is experienced in performing the procedure. Subjects,

or their designated decision maker, will call the investigator to report any adverse events associated with the LP procedure.

7.1.3. Initial PET Imaging Visits:

Subjects who qualify will have a florbetapir F 18 PET imaging session and their initial ¹⁸F-AV-1451 PET imaging session. The imaging sessions must be performed at least 48 hours apart, but not more than 60 days apart. The order of the scans is interchangeable.

Florbetapir F 18 PET Imaging Session

- For women of childbearing potential, a negative urine pregnancy test must be obtained within 24 hours prior to injection;
- A physician or physician designee must see the subject prior to administration of Florbetapir F 18 Injection to determine if they are still suitable to undergo the scan;
- Vital signs will be taken (pulse rate, respiratory rate, supine blood pressure, and weight) immediately prior to injection of florbetapir F 18;
- Subjects will receive a single IV bolus injection of approximately 370 MBq (10 mCi) +10% of florbetapir F 18 followed by a saline flush. A 10-minute(2 acquisitions of 5 minute duration) continuous, dynamic PET brain scan will begin approximately 50 minutes following the dose administration;
- A physician or physician designee will see the subject prior to discharge from the imaging center to evaluate the subject's readiness for discharge;

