7.1.4. First and Second Longitudinal Follow-up Visits

Exploratory Phase: The first and second follow-up visits will consist of PET scan procedures, an MRI, cognitive assessments and updated medical history and concomitant medications. The first follow-up scan will occur 9 (+/-2) months following the subject's initial ¹⁸F-AV-1451 scan. The second follow up scan will occur 18 (+/-2) months following the initial ¹⁸F-AV-1451 scan. The cognitive assessments and MRIs should be performed +/- 30 days of each corresponding ¹⁸F-AV-1451 PET imaging visit and within

the 9 (+/-2) months window. The cognitive assessments and MRI should take place in the same 30 day window.

Confirmatory Phase Cohort: The first and second follow-up visits will consist of cognitive assessments and updated medical history and concomitant medications. The first follow-up visit will occur 9 (+/-2) months following the subject's initial ¹⁸F-AV-1451 scan. The second follow-up visit will occur 18 (+/-2) months following the initial ¹⁸F-AV-1451 scan.

Cognitive Assessments: Raters administering the below assessments will be blinded to the ¹⁸F-AV-1451 scans for subjects in the Confirmatory Cohort

- Mini Mental State Exam (MMSE);
- Alzheimer's Disease Assessment Scale- Cognitive subscale (ADAS-Cog11);
- Neuropsychological test battery (Digit Symbol Substitution Test (DSST), Digit span forward and backward ,Trail Making A and B, Logical Memory Test, Immediate and Delayed Recall Story A , Animal list generation, Boston Naming Test (BNT) (30 item), American National Adult Reading Test (ANART), Clock Drawing Test, Benton Judgment of Line Orientation test);
- Clinical Dementia Rating (CDR) Scale; For the MCI and AD groups only.
- Pfeffer Functional Activities Questionnaire (FAQ). For the MCI and AD groups only.

Magnetic Resonance Imaging (MRI) (for Exploratory Phase cohort only)

MRI, including both volumetric and standard clinical sequences, will be obtained at the first and second follow-up visits.

¹⁸F-AV-1451 PET Imaging Session (for Exploratory Phase cohort only)

The first follow-up scan will occur 9 (+/-2) months following the subject's initial ¹⁸F-AV-1451 scan. The second follow up scan will occur 18 (+/-2) months following the initial ¹⁸F-AV-1451 scan. Procedures for the longitudinal follow-up scans will be identical to the initial scan:

- A physician must see the subject prior to administration of ¹⁸F-AV-1451 Injection to determine if they are still suitable to undergo the scan;

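### Confirmatory Cohort rater blinding is specified for the tau scan only; florbetapir results should be covered too

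*Protocol*

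**What the plan says.** The protocol states rater blinding in five places, each time for one scan.

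- Section 5.1, and the synopsis under Study Design in the same terms: "Raters administering the cognitive testing will be blinded to the" ¹⁸F-AV-1451 scans, for Confirmatory Cohort subjects.
- Section 7.1.1 (screening and baseline): "Raters administering the MMSE and baseline assessments described below will be blinded to the ¹⁸F-AV-1451 scans for subjects in the Confirmatory Cohort".
- Section 7.1.3 repeats this at the head of the tau imaging session.
- Section 7.1.4 (9 and 18 months): "Raters administering the below assessments will be blinded to the ¹⁸F-AV-1451 scans for subjects in the Confirmatory Cohort". The list that follows includes MMSE, ADAS-Cog11, the neuropsychological battery, CDR and FAQ.

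For the sponsor's own staff the scope is wider. Section 5.1 says "Avid personnel will also remain blinded to the PET scans (both florbetapir and ¹⁸F-AV-1451) performed on subjects in the Confirmatory Phase", apart from limited quality checks, and also blinds those staff to the confirmatory longitudinal cognitive data.

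On the outcome, Section 8.1.1.2 leaves the final hypothesis and endpoints open, and Section 8.1.4 says the progression truth standard will be picked from exploratory findings. The supplied SAP covers the exploratory phase only; its Section 4.4 leaves confirmatory blinding to a later SAP.

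**The concern.** The confirmatory question is whether the baseline tau scan predicts progression over 18 months. Its answer is unbiased only if the outcome is scored without knowledge of the test, or of anything that stands in for the test. Amyloid status could be such a stand-in. The protocol's introduction treats a negative florbetapir scan as speaking against AD, so a rater who knows the result may expect more or less decline. The exploratory SAP (8.6.2.4.1) combines amyloid and tau reads into one three-level predictor of cognitive change. If the two statuses overlap and expectation affects scoring, the tau scan could look more accurate than it is although no rater has seen it.

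**Working it through.** **Can a rater know the amyloid result under the plan as written?**

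1. All confirmatory subjects have florbetapir PET (7.1, 7.1.3).
2. On timing, 7.1.3 says "The order of the scans is interchangeable", with at most 60 days between scans. Baseline testing may fall 30 days either side of the tau scan (7.1.1). Florbetapir can therefore precede baseline testing, and by design it precedes the 9- and 18-month ratings.
3. Image copies stay at the site or imaging center (7.6).
4. No sentence in either document withholds the florbetapir result from raters.

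So the plan permits such knowledge. It does not provide for it.

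**How large could the bias be?** The documents give no figure to reproduce, so this is an illustration on assumed inputs.

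- q = true progression rate: 40%, with 20% as a check.
- a₁, a₀ = amyloid positivity in tau-positive and tau-negative subjects. Strong link: 95% and 40%. Weak link: 80% and 50%. Amyloid is taken to depend on tau status only.
- e = share of disagreeing outcomes moved toward the amyloid result: amyloid-positive non-progressors recorded as progressed, and amyloid-negative progressors recorded as stable.

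For a subject with amyloid probability a, P(recorded progression) = 1 − (1 − a)e for a true progressor and a·e for a true non-progressor.

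Plausibility: with half of subjects tau-positive, overall amyloid positivity is (0.95 + 0.40)/2 = 67.5% or (0.80 + 0.50)/2 = 65%. Both lie between the 50% (MCI) and 80% (AD) planning rates in Section 8.1.1.1.

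Worked case: uninformative scan (50%/50%), q = 0.40, strong link, e = 0.10.

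- True progressors, 0.20 of subjects in each tau group. Recorded as progressed: tau-positive 0.20 × 0.995 = 0.1990; tau-negative 0.20 × 0.94 = 0.1880.
- True non-progressors, 0.30 in each tau group. Recorded as progressed: tau-positive 0.30 × 0.095 = 0.0285; tau-negative 0.30 × 0.04 = 0.0120.
- Apparent sensitivity = (0.1990 + 0.0285)/(0.2275 + 0.2000) = 53.2%.
- Recorded as stable: tau-positive 0.001 + 0.2715 = 0.2725; tau-negative 0.012 + 0.288 = 0.3000. Apparent specificity = 0.3000/0.5725 = 52.4%.
- Share of all outcomes altered = 0.001 + 0.012 + 0.0285 + 0.012 = 5.35%.

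Apparent sensitivity/specificity (%):

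| True | q | Link | e = 5% | e = 10% | e = 20% |
|---|---|---|---|---|---|
| 50/50 | 40% | strong | 51.7/51.2 | 53.2/52.4 | 56.0/55.0 |
| 60/60 | 40% | strong | 60.7/60.9 | 61.4/61.9 | 62.5/64.0 |
| 65/65 | 40% | strong | 65.2/65.8 | 65.4/66.7 | 65.8/68.5 |
| 60/60 | 20% | strong | 60.7/60.8 | 61.3/61.6 | 62.3/63.4 |
| 50/50 | 40% | weak | 50.9/50.6 | 51.8/51.3 | 53.3/52.7 |
| 60/60 | 40% | weak | 60.0/60.4 | 59.9/60.8 | 59.9/61.7 |
| 65/65 | 40% | weak | 64.5/65.3 | 64.0/65.5 | 63.2/66.1 |
| 60/60 | 20% | weak | 59.4/60.4 | 58.9/60.8 | 58.1/61.7 |

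At e = 5–10% under the strong link, the gains are 0.7 to 3.2 points for a scan at 50/50 or 60/60 and 0.2 to 1.7 points at 65/65. Under the weak link the changes run from −1.1 to +1.8 points.

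**The case against.** The best defence is that the documents are silent, not permissive. A reader might infer that raters are unblinded to florbetapir or will be shown the result. The text does not support that: no passage provides for a site amyloid read or for returning a result to raters, Section 5.1 has the imaging core laboratory manage the scans, and image copies are kept locally for both tracers. This stands, and it limits the point to an unstated protection.

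Three other tempting readings also go too far.

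- That the truth standard is ADAS-Cog or CDR. It is still open. The candidates differ in exposure: MMSE and ADAS-Cog are scored largely on performance, FAQ comes from the informant, and CDR leaves the most to judgement.
- That tau-positive subjects are mostly amyloid positive. Neither document gives a proportion, and SAP 8.6.1.3.2 lists the amyloid–tau correlation as an analysis to be done.
- That accuracy must be inflated. Under the weak link sensitivity can fall. A constant scoring shift at both baseline and follow-up would cancel in the change score.

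The comparison with sponsor staff shows no contradiction, since they are a different group with a different role. It does show that florbetapir was considered when blinding was planned.

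The deferral to a confirmatory SAP does not answer the point. Protocol 8.1.4 requires that SAP to be final only before database lock, and blinding lost while ratings are being collected cannot be restored afterwards.

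**Conclusion.** The gap is real and modest. Rater blinding is specified for the tau scan alone, and a site could follow the protocol exactly while its raters know amyloid status. On the assumed inputs the bias is about 1 to 3 points under a strong amyloid–tau link with 5–10% of disagreeing outcomes shifted, and little or none under a weak link. It generally favours the tau scan. The planned criterion is at least 70% for both measures with lower 95% bounds above 50%. Even at e = 20% an uninformative scan averages only 56%/55%, so this mechanism alone would not be expected to carry such a scan to the target. It would still erode confidence in a result near the margin. The size rests on the overlap and on the degree of rater influence, and the documents give neither. This is a cheap improvement, not a flaw that undermines the design.

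**What to change.** In the synopsis (Study Design) and Sections 5.1, 7.1.1, 7.1.3 and 7.1.4, state that Confirmatory Cohort raters are blinded to the ¹⁸F-AV-1451 and florbetapir F 18 scans and to their results, at baseline, 9 and 18 months. Change all five together so that they agree, and carry the rule into the confirmatory SAP that SAP 4.4 refers to. No extra raters, visits or procedures are needed. The one cost is that sites must keep a second scan result from the raters; where they already do so, the change only documents it.
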